4.4 Withdrawal of Patients from Treatment

Patients should be removed from therapy if any of the following occurs:

- Disease progression. Every effort should be made to document objective evidence of tumor progression.
- The occurrence of unacceptable toxicity indicating the need for cessation of treatment.
- The physician feels it is in the best interest of the patient to stop treatment.
- Patient refusal to continue with therapy.
- Non-compliance by the patient with protocol requirements.
- Patient is lost to follow-up. If a patient does not return for scheduled visits, every effort should be made to re-establish contact. In any circumstance, every effort should be made to document patient outcome, if possible.
- Patient becomes pregnant.
- Termination of the study by investigator or Sponsor – M. D. Anderson Cancer Center.

5.0 TREATMENT PLAN

This is a Phase II open label study of combination therapy with RAD001 and letrozole in patients with progressive or recurrent endometrial cancer. The initial dose of RAD001 is 10 mg daily and the dose of letrozole is 2.5 mg daily, both given orally.

5.1 Multi-Center Patient Registration Procedures: All patients from Morristown and M. D. Anderson will be registered in CORE at University of Texas, MD Anderson Cancer Center.

Centralized Registration Requirements: Patients who are candidates for the study will first be evaluated for eligibility by the local investigator. All patients must be registered both locally and centrally with MDACC.

Before an institution may begin participating in a MDACC sponsored protocol that is coordinated by MDACC, they must complete the following steps:

- Submit the following required regulatory documents to the MDACC Office of Multicenter Clinical Research (OMCR)
- Participate in a site initiation visit, webcast, or conference call
- Receive training regarding study specific CRF's and/or databases
- Execute study specific contractual agreements

After these requirements have been fulfilled, the participating institution will receive by fax, e-mail, or hard copy memo a Site Activation Notification. Once the Site Activation Notification has been received, the participating institution may begin to register patients to the protocol.

Required Regulatory Documents include:

- ✓ FDA 1572
- ✓ Curriculum Vitae (CV) or Biosketch. The CV/Biosketch must be submitted with the individual's signature and date.
- ✓ Delegation of Authority Log (DAL)
- ✓ Approval Letter signed by the Chairman of the institution's IRB (must be updated annually. Patient registrations will be suspended for expired IRB approvals)
 - An Expedited IRB first approval is NOT acceptable
 - IRB Approval for amendments

Informed Consent/Authorization

Prior to protocol enrollment and initiation of treatment, subjects must sign and date an Institutional Review Board (IRB) approved consent form.

Patient Registration Procedures

M. D. Anderson Cancer Center (MDACC) patients will be registered in The Clinical Oncology Research System (CORe) by department of Gynecology staff. Participating institutions must register patients via phone, fax, and/or email with the MDACC Office of Multicenter Clinical Research at:

[contact]
[contact]
Email: [contact]

Registration hours are 8:00 a.m. to 5:00 p.m. Central Standard Time, Monday through Friday, except holidays.

Registration is a 2-step process. Step 1 - Initial registration must be completed:

- After the patient has signed the informed consent and has been determined to be eligible by the local investigator.

Once eligibility has been determined, Step 2 is treatment assignment -

- Before study related treatment is initiated.

At the time of registration the following information will be requested by the MDACC Office of Multicenter Clinical Research (OMCR):

- A faxed or emailed copy of a completed and signed, protocol specific, eligibility checklist form
- One copy of a Pathology report from the patient's most recent surgery or biopsy
- One copy of the signed and dated Informed Consent/Authorization.

The eligibility checklist should be prepared and signed prior to faxing or emailing to the MDACC OMCR. The fax/email should be followed by a phone call to the MDACC OMCR to verify receipt.

If the patient fails eligibility screening do not proceed to the MDACC registration process.

Patient Number for Participating Institutions

Once eligibility has been established during Registration, the patient from the participating institution is assigned a six character MDACC OMCR patient number. This number is unique to the patient and must be written on all data and correspondence for the patient.

Verification of Registration

For participating institutions, a Registration Verification Letter for patients registered will be faxed or emailed to the registering institution within one working day after registration.

Initiation of Therapy

Treatment may not be initiated until the participating institution receives a faxed or emailed copy of the patient's Registration Verification Letter from the MDACC OMCR. Patients must initiate treatment within 10 calendar days after the registration is completed.

The MDACC OMCR must be notified in writing of any exceptions to this policy.

Eligibility Exceptions: Eligibility Exceptions will not be granted.

Confidentiality: All documents, investigative reports, or information relating to the patient are strictly confidential. Any patient specific reports (i.e. Pathology Reports, MRI Reports, Operative Reports, etc.) submitted to the MDACC OMCR must have the patient's full name & social security number "blacked out" and the assigned MDACC patient ID number and protocol number written in. Patient initials may be included or retained for cross verification of identification.

5.2 RAD001 and letrozole administration

- 5.2.1 Both study medications will be dispensed by the pharmacy. Study medication will be supplied in an open label fashion. Patients will self administer the both medications at home.
- 5.2.2 Patients will be instructed to take the study medication at a consistent time each day.
- 5.2.3 RAD001 is formulated as tablets of 5 mg strength and supplied in blister packs under aluminum foil, which should be opened only at the time of administration as drug is both hygroscopic and light-sensitive. Two 5 mg tablets should be taken orally once daily in a fasting state or after no more than a light, fat-free meal. Avoid grapefruit-containing products during the treatment period.
- 5.2.4 Letrozole is formulated as tablets of 2.5 mg and supplied in bottles. The dose of letrozole is one 2.5 mg tablet administered orally once daily. The oral single dose of RAD001 should be taken together with the daily dose of letrozole 2.5 mg.
- 5.2.5 Each cycle will consist of 4 weeks of therapy. Patients will be seen prior to each cycle. To allow for holidays, vacations and other important life events, patients may be seen +/- 7 days of their return visit date. Any other schedule modifications must be approved by

the study chair. In these circumstances, patients may be dispensed additional medication in order not to interrupt treatment.

- 5.2.6 After the second cycle (8 weeks \pm 7 days), patients will undergo a radiologic evaluation using the same imaging technique that was used during the initial evaluation (i.e., CT or MRI) unless clinical suspicion warrants earlier evaluation.
- 5.2.7 For the duration that patients are on study therapy, adverse event monitoring will be done continuously. Patients will be evaluated for adverse events at each physician visit and are to be instructed to call their physician to report any clinically significant adverse events between visits.

5.3 Dose modifications / Management of Adverse Reactions

Toxicity will be assessed using the NIH-NCI Common Terminology Criteria for Adverse Events, version 3.0 (CTCAEv3.0, (<http://ctep.cancer.gov/forms/CTCAEv3.pdf>)).

Dose Modification Table:

Dose level	-2	-1	0
RAD001	Off study	5 mg daily	10 mg daily
Letrozole	Off study	2.5 mg daily	2.5 mg daily

Patients will be removed from study for any:

- grade 4 treatment-related toxicity (assuming that appropriate preventive therapy has been given where possible – e.g. antiemetic therapy in case of vomiting, lipid-lowering drug in case of hyperlipidemia), or
- hematologic or non-hematologic toxicity requiring interruption of one or both drugs for > 3 weeks. For detailed recommendations on dose interruption and modification due to suspected toxicity, please refer to the following table.

**Algorithm for interpretation and dose modification
 due to suspected treatment related toxicity:**

Treatment-related toxicity	Actions
Non-hematological toxicity	
Grade 2 (except fatigue, hyperlipidemia, and non-infectious pneumonitis – see Dose Modification Table, page 30)	For first occurrence, interrupt RAD001 (continue letrozole) until recovery to grade ≤ 1 then reintroduce RAD001 (no dose reduction). If the event recurs, interrupt study treatment (Letrozole and RAD001) until recovery to grade ≤ 1 then reintroduce therapy at -1 dose level. If the event recurs a 3 rd time, remove patient from study.
Grade 3 (except hyperlipidemia and non-infectious pneumonitis)	For first occurrence, interrupt study treatment (Letrozole and RAD001) until recovery to grade ≤ 1 . Then reintroduce therapy at -1 dose level. If the event recurs remove from study. For pneumonitis consider the use of a short course of corticosteroids.
Grade 4	Remove from study.

Lipid-lowering drugs

Increased lipid levels are a known adverse effect of treatment with both RAD001 and aromatase inhibitors. In case of hyperlipidemia (\geq grade 1 hypercholesterolemia with or without hypertriglyceridemia), in addition to dietary advice to patients, an HMG-CoA reductase inhibitor such as atorvastatin, pravastatin or fluvastatin may be associated with study treatment.

Hematological toxicity	
Grade 2 Thrombocytopenia (platelets <75 , $\geq 50 \times 10^9/L$)	
Interrupt study treatment (Letrozole and RAD001) until recovery to grade ≤ 1 ($>75 \times 10^9/L$) then resume study treatment (no dose reduction).
 
If the grade 2 thrombocytopenia recurs, interrupt study treatment (Letrozole and RAD001) until recovery to grade ≤ 1 then reintroduce therapy at -1 dose level.
 
If the event recurs a 3rd time, remove patient from study.

Grade 3 Thrombocytopenia (platelets <50 , $\geq 25 \times 10^9/L$)	
Interrupt study treatment (Letrozole and RAD001) until recovery to grade ≤ 1 (platelets $\geq 75 \times 10^9/L$) then resume study treatment at the -1 dose level.
 
If grade 3 thrombocytopenia recurs, remove from study.

Grade 4 Thrombocytopenia (platelets $< 25 \times 10^9/L$)	Remove from study
Grade 3 Neutropenia (neutrophils <1 , $\geq 0.5 \times 10^9/L$)	
Interrupt study treatment (Letrozole and RAD001) until recovery to grade ≤ 1 then resume study treatment (no dose reduction).
 
If ANC again returns to Grade 3, hold study treatment (Letrozole and RAD001) until the ANC $\geq 1.5 \times 10^9/L$ then resume study treatment (Letrozole and RAD001) at the -1 dose level.
 
Remove from study for a third episode of grade 3 neutropenia.

Grade 4 Neutropenia (neutrophils $< 0.5 \times 10^9/L$)	
Interrupt study treatment (Letrozole and RAD001) until recovery to grade ≤ 1 (neutrophils $\geq 1.5 \times 10^9/L$) then resume study treatment (Letrozole and RAD001) at the -1 dose level.
 
Remove from study if grade 4 neutropenia reoccurs despite this dose reduction.

Grade 3 febrile neutropenia (not life-threatening)	
Interrupt study treatment (Letrozole and RAD001) until resolution of fever and neutropenia to grade ≤ 1 and hold further study treatment (Letrozole and RAD001) until the ANC $\geq 1,500/mm^3$ and fever has resolved. Then resume study treatment (Letrozole and RAD001) at the -1 dose level.
 
If febrile neutropenia recurs, remove from study.

Grade 4 febrile neutropenia (life-threatening)	Remove from study
Any hematological or non-hematological toxicity requiring interruption for ≥ 3 weeks	Remove from study

5.3.1 Management of non-infectious pneumonitis:

Non-infectious pneumonitis is a class effect of rapamycin derivatives. Cases of non-infectious pneumonitis (including interstitial lung disease) have also been described in patients taking everolimus (see Section 5 Adverse drug reactions). Some of these have been severe and on rare occasions, a fatal outcome was observed.

A diagnosis of non-infectious pneumonitis should be considered in patients presenting with non-specific respiratory signs and symptoms such as hypoxia, pleural effusion, cough or dyspnoea, and in whom infectious, neoplastic and other non-medicinal causes have been excluded by means of appropriate investigations. Patients should be advised to report promptly any new or worsening respiratory symptoms.

Patients who develop radiological changes suggestive of non-infectious pneumonitis and have few or no symptoms may continue everolimus therapy without dose alteration. If symptoms are moderate (Grade 2), consideration should be given to interruption of therapy until symptoms improve. The use of corticosteroids may be indicated. Everolimus may be reintroduced at a reduced dose until recovery to Grade 1 or better.

For cases where symptoms of non-infectious pneumonitis are severe (Grade 3), everolimus therapy should be discontinued and the use of corticosteroids may be indicated until clinical symptoms resolve. Therapy with everolimus may be re-initiated at a reduced dose depending on the individual clinical circumstances.

Worst Grade Pneumonitis	Required Investigations	Management of Pneumonitis	Everolimus Dose Adjustment
Grade 1	CT scans with lung windows and pulmonary function testing including: spirometry, DLCO, and room air O ₂ saturation at rest. Repeat chest x-ray/CT scan every 2 Cycles until return to baseline.	No specific therapy is required	Administer 100% of everolimus dose.
Grade 2	CT scan with lung windows and pulmonary function testing including: spirometry, DLCO, and room air O ₂ saturation at rest. Repeat each subsequent Cycle until return to baseline. Consider bronchoscopy*	Symptomatic only. Prescribe corticosteroids if cough is troublesome.	Reduce everolimus dose until recovery to ≤ Grade 1. Everolimus may also be interrupted if symptoms are troublesome. Patients will be withdrawn from the study if they fail to recover to ≤ Grade 1 within 3 weeks.
Grade 3	CT scan with lung windows and pulmonary function testing including: spirometry, DLCO, and room air O ₂ saturation at rest; Repeat each subsequent Cycle until return to baseline. Bronchoscopy is recommended*	Prescribe corticosteroids if infective origin is ruled out. Taper as medically indicated.	Hold treatment until recovery to ≤ Grade 1. May restart protocol treatment within 2 weeks at a reduced dose (by one level) if evidence of clinical benefit. Patients will be withdrawn from the study if they fail to recover to ≤ Grade 1 within 2 weeks.
Grade 4	CT scan with lung windows and required pulmonary function testing includes: spirometry, DLCO, and room air O ₂ saturation at rest. Repeat each subsequent Cycle until return to baseline. Bronchoscopy is recommended*.	Prescribe corticosteroids if infective origin is ruled out. Taper as medically indicated.	Discontinue treatment.

*A bronchoscopy with biopsy and/or bronchoalveolar lavage is recommended.

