5.5 Supportive Care Guidelines/Concomitant Medications

5.5.1 Growth Factors: Routine prophylactic use of growth factors is not permitted. However, therapeutic use in patients with serious hematologic complications such as sepsis may be considered at the investigator's discretion.

[figure not shown]
5.5.2 Antiemetics: The use of antiemetics will be left to the investigator's discretion.

5.5.3 Other Concomitant Medications: In general, concomitant medications and therapies deemed necessary for the supportive care and safety of the patient are allowed, provided their use is documented in the patient record. The administration of any other anticancer agents including chemotherapy and biologic agents is NOT permitted. Similarly, the use of other concurrent investigational drugs is not allowed.

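### Section 5.3 removes patients for any grade 4 treatment-related toxicity, yet its own table resumes treatment after a first grade 4 neutropenia, and no order of precedence is stated

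*Combined protocol and SAP*

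**What the plan says.** Section 5.3 of the combined protocol and SAP opens with a short removal list. Its lead-in is "Patients will be removed from study for any", and the first item is "grade 4 treatment-related toxicity (assuming that appropriate preventive therapy has been given where possible". The second item is "hematologic or non-hematologic toxicity requiring interruption of one or both drugs for > 3 weeks". The list then hands over to the dose-modification algorithm: "For detailed recommendations on dose interruption and modification due to suspected toxicity, please refer to the following table".

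In that algorithm, the Grade 4 Neutropenia row interrupts both drugs until recovery, "then resume study treatment (Letrozole and RAD001) at the -1 dose level". Removal comes only later: "Remove from study if grade 4 neutropenia reoccurs despite this dose reduction". The last row of the same table sends patients off study for "Any hematological or non-hematological toxicity requiring interruption for ≥ 3 weeks".

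Section 5.5.1 states: "Routine prophylactic use of growth factors is not permitted".

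Section 5.3.2, Table 3-3, has its own rule for hepatitis B reactivation. Study drug is interrupted, then restarted if the reactivation resolves within 28 days and discontinued if it takes longer. The table does not say from which date the 28 days are counted. Its footnote defines a date of viral reactivation but does not tie the limit to it.

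**The concern.** A first grade 4 neutropenia judged treatment-related falls under two instructions that cannot both be followed. The list removes the patient; the table brings her back on treatment after recovery. Both govern the same class of event, since the algorithm is also headed as applying to suspected treatment-related toxicity.

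The issue is resumption. Section 4.4 always lets the physician stop treatment, so stopping never breaches the protocol. A site that resumes as the neutropenia row directs does breach the removal list as written. With two sites enrolling (Section 3), identical patients could be managed in opposite ways, each site citing Section 5.3. That is a matter of patient safety and uniform conduct first. Any effect on who enters the CR + PR + SD analysis comes second.

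**Working it through.** There is no plan figure to reproduce. The check compares texts, with some day counts and one bound.

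**1. Grade 4 events, list against table (Section 5.3)**

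| Event | Removal list | Table row | Agree? |
|---|---|---|---|
| Grade 4 non-hematological | remove | remove | yes |
| Grade 4 thrombocytopenia | remove | remove | yes |
| Grade 4 febrile neutropenia | remove | remove | yes |
| Grade 4 neutropenia, first | remove | interrupt, then resume one level lower | **no** |
| Grade 4 neutropenia, recurrent | remove | remove | yes |

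Neutropenia is the only departure, and it is not marked as an exception. The exceptions that the table does name (fatigue, hyperlipidemia, non-infectious pneumonitis) stand in its Grade 2 and Grade 3 non-hematological rows. The removal list names none.

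**2. Does the preventive-therapy qualifier reconcile them?** Its examples are antiemetics and lipid-lowering drugs. For neutropenia, routine growth-factor prophylaxis is ruled out by Section 5.5.1, and the neutropenia row carries no such condition. The qualifier therefore does not clearly exempt a first episode.

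**3. Interruption limits.** Take 3 weeks = 21 days. The list removes when the interruption exceeds 21 days, so from day 22. The table removes from day 21. For Table 3-3, assume the 28 days start when drug is interrupted.

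| Length of interruption | List (> 21 days) | Table (≥ 21 days) | Table 3-3 (clock assumed to start at interruption) |
|---|---|---|---|
| up to 20 days | stay | stay | restart |
| 21 days | stay | remove | restart |
| 22 to 28 days | remove | remove | restart |
| 29 days or more | remove | remove | discontinue |

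The list and the table differ at one value, day 21. Table 3-3 conflicts with both on 28 − 22 + 1 = 7 day values. The general limits plausibly reach hepatitis B because the Table 3-3 footnote records reactivation as a CTCAE grade 3 or 4 event. If the clock started a week before interruption, the longest interruption still restarted would be 28 − 7 = 21 days, and the conflict on days 22 to 28 would vanish. If it started after interruption, the overlap would be longer.

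**4. How often might a first grade 4 neutropenia occur?** Inputs:
- Section 1.4.4.3: abnormal counts were adverse events in four phase 1 monotherapy patients. The only neutropenia was grade 3. The study tables in Section 1.4.4.2 give 84 patients.
- Section 1.4.4.2: in the phase III renal trial (everolimus n = 274), neutropenia is not among the grade 3-4 reactions with incidence of at least 2%.
- Section 1.5: any-grade neutropenia was 40% of 35 patients, or 14, in the single-agent endometrial trial. No grade 4 rate is given.

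The exact one-sided 95% upper bound for 0 of 84 is 1 − 0.05^(1/84) = 0.035. At that bound, the maximum of 42 enrolled patients (Section 10) would yield 42 × 0.035 = 1.5 expected cases.

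Caveats: the 84 patients had mixed weekly and daily schedules, only 13 took 10 mg daily, and the counts are adverse-event reports. The renal trial is in another tumor, and laboratory values may have been tabulated separately.

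**5. Reach into the efficacy population.** Section 10.1 makes patients who come off treatment for reasons other than progression, before response is established, evaluable for toxicity only. The first scan is at week 8. Stable disease needs repeat studies at least 8 weeks later (Section 6.3), so week 8 + 8 = 16. Only removals before then matter. Even then, a patient with one cycle and an end-of-treatment scan (Section 6.4) can meet the evaluability definition in Section 7.1.1.

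**The case against.** The strongest reply is that the specific row overrides the general list. Section 5.3 itself sends the reader to the table for detail, the neutropenia row is explicit, treatment stops at once under either text, and resumption waits for neutrophil recovery. This is a natural reading and may be what was meant. But the pointer offers detail without saying that the table may override a removal rule, and every other grade 4 row follows the list. The reading is possible, not stated. The objection narrows the practical risk without removing the contradiction.

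It is also fair that the > / ≥ mismatch is a single day value and that reactivation is described as sporadic (Section 1.4.4.2), with no rate.

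Four stronger readings are tempting, and the documents do not support them:
- A reader might infer that the hepatitis B rule conflicts outright with the 3-week limits. It does so only under an assumed start for the 28 days.
- A reader might infer a further conflict for a life-threatening reactivation recorded as grade 4, since Table 3-3 does not distinguish grades. That needs the event to be life-threatening, judged treatment-related and resolved in time for a restart. The chain is too long to rest a finding on.
- A reader might infer from the letrozole combination study (Section 1.7.3) that grade 4 neutropenia could be common. None among the 15 patients of Table 1-5 has an upper bound of 1 − 0.05^(1/15) = 18%; if only the 11 patients documented there count, 1 − 0.05^(1/11) = 24%. These bounds are wide because the sample is small and are not evidence of a high rate. The larger monotherapy data point to a lower one.
- A reader might infer bias in the CR + PR + SD rate. None is shown.

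**Conclusion.** Wrong as written: an internal contradiction, not a design choice. For a first grade 4 neutropenia, the removal list and the table in Section 5.3 give opposite outcomes, and no text says which prevails. This rests on the wording alone and needs no assumption beyond the event being judged treatment-related.

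The disagreement over the interruption limit is certain but minor. The hepatitis B conflict is conditional on the 28 days running from drug interruption.

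The number of patients affected cannot be fixed, because no grade 4 neutropenia rate is given for this combination. The available data suggest that such events are probably uncommon, subject to the caveats above. The case for correction is that two sites need one instruction for each event. Any effect on the primary analysis is secondary and not shown to be material. It should be fixed, but it does not threaten the trial's conclusion.

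**What to change.** The clinical lead should reconcile the removal list and table in Section 5.3 with Table 3-3 in Section 5.3.2, so that each of these has one outcome: a first grade 4 neutropenia, an interruption of exactly 3 weeks, and a hepatitis B interruption lasting beyond 3 weeks and up to 28 days. Either name the exceptions in the removal list or state which text takes precedence. Use one inequality sign for the interruption limit in both places, and state the date from which the 28 days are counted. No view is taken here on which clinical rule is right.

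The cost is a protocol wording amendment. Sample size, stopping rule and analysis are unaffected.

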5.3.5 INDUCERS & INHIBITORS OF CYP3A4 AND/OR PgP and OTHER RELEVANT DRUG INTERACTIONS

Table 3-5 Inducers/Inhibitors of CYP3A4 and/or PgP

Inhibitors of CYP3A4 and/or PgP
 
Co-administration with strong inhibitors of CYP3A4 (e.g., ketoconazole, itraconazole, ritonavir) or P-glycoprotein (PgP) should be avoided.
 
Co-administration with moderate CYP3A4 inhibitors (e.g., erythromycin, fluconazole) or PgP inhibitors should be used with caution. If patient requires co-administration of moderate CYP3A4 inhibitors or PgP inhibitors, reduce the dose of everolimus to half the currently used dose e.g., 10mg daily would be reduced to 5mg daily. Additional dose reductions to every other day may be required to manage toxicities. If the inhibitor is discontinued the everolimus dose should be returned to the dose used prior to initiation of the moderate CYP3A4/PgP inhibitor.
 
Seville orange, star fruit, grapefruit and their juices affect P450 and PgP activity. Concomitant use should be avoided.

Inducers of CYP3A4 and/or PgP
 
Avoid the use of strong CYP3A4 inducers. If patient requires co-administration of strong CYP3A4 inducers (i.e., phenytoin, carbamazepine, rifampin, rifabutin, phenobarbital, St. John's wort), an increase in the dose of everolimus up to twice the currently used daily dose should be considered, using 5mg increments. Enzyme induction usually occurs within 7-10 days, therefore everolimus dose should be increased by one increment 7 days after the start of the inducer therapy. If no safety concerns are seen within the next 7 days, the dose can be increased again one additional increment up to a maximum of twice the daily dose used prior to initiation of the strong CYP3A4 inducer.
 
This dose adjustment of everolimus is intended to achieve similar AUC to the range observed without inducers. However, there are no clinical data with this dose adjustment in patients receiving strong CYP3A4 inducers. If the strong inducer is discontinued the everolimus dose should be returned to the dose used prior to initiation of the strong CYP3A4/PgP inducer.

Table 3-6
Clinically relevant drug interactions: substrates, inducers, and inhibitors of isoenzyme CYP3A

SUBSTRATES	
Antibiotics: Clarithromycin, erythromycin, telithromycin	Calcium channel blockers: Amlodipine, diltiazem, felodipine, lercanidipine, nifedipine, nisoldipine, nitrendipine, verapamil

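### Level -1 is a fixed 5 mg daily that is not reconciled with Table 3-5: the 5.3 algorithm alone gives no toxicity cut to a patient already halved for a moderate inhibitor, and the return rule can undo the reduction

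*Combined protocol and SAP*

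**What the plan says.** The dose modification table in section 5.3 has three RAD001 levels: 10 mg daily (level 0), 5 mg daily (level -1) and off study (level -2). The levels are absolute doses. The algorithm below it sends patients to level -1 after specified toxicities. For a first grade 3 non-hematological event (hyperlipidemia and non-infectious pneumonitis excepted) it says "Then reintroduce therapy at -1 dose level. If the event recurs remove from study". For a first grade 3 thrombocytopenia, treatment is held until recovery and "then resume study treatment at the -1 dose level". The grade 4 neutropenia row ends "Remove from study if grade 4 neutropenia reoccurs despite this dose reduction", so its authors regarded the move to level -1 as a reduction.

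Table 3-5 in section 5.3.5 covers drug interactions. If a moderate CYP3A4 inhibitor or a PgP inhibitor is needed, the site must "reduce the dose of everolimus to half the currently used dose e.g., 10mg daily would be reduced to 5mg daily". The table continues "Additional dose reductions to every other day may be required to manage toxicities", and then "If the inhibitor is discontinued the everolimus dose should be returned to the dose used prior to initiation of the moderate CYP3A4/PgP inhibitor".

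Section 5.2.3 states that "RAD001 is formulated as tablets of 5 mg strength". Section 5.6.2 lists a 2.5 mg tablet among the dosage forms, but 5.2.3 does not supply it.

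**The concern.** A patient can reach 5 mg daily by two routes: toxicity (level -1) or an interacting drug (Table 3-5). The plan does not say what happens when both apply. If 5 mg is already her interaction-adjusted dose, an instruction to restart at level -1 leaves the dose unchanged. She is rechallenged at the dose on which the event occurred and is removed if it recurs, without the reduced-dose attempt that a 10 mg patient gets.

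The return rule adds a second problem. It looks back to the dose before the inhibitor, not to the level assigned since. A toxicity in between leaves no mark on the dose to which she returns.

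The stakes are dosing safety and consistency between the two sites, which could treat the same patient differently and each point to the text.

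**Working it through.** **Inputs.** Level 0 is 10 mg daily and level -1 is 5 mg daily (5.3). With a moderate inhibitor the current dose is halved, and every-other-day dosing is allowed for toxicity (Table 3-5). The tablet supplied is 5 mg (5.2.3).

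**Formula.** Cut = 1 - (new average daily dose / current average daily dose).

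**Plan's own example.** 10 × 0.5 = 5 mg daily, as Table 3-5 states.

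| Situation | Dose before | Dose after | Cut |
|---|---|---|---|
| No inhibitor, sent to level -1 | 10 mg daily | 5 mg daily | 1 - 5/10 = 50% |
| Moderate inhibitor, 5.3 followed alone | 5 mg daily | 5 mg daily | 1 - 5/5 = 0% |
| Moderate inhibitor, every-other-day step used | 5 mg daily | 5 mg every other day (average 2.5 mg/day) | 1 - 2.5/5 = 50% |

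**Rows affected.** Seven rows of the 5.3 algorithm restart at level -1.
- Four do so at the first event: grade 3 non-hematological, grade 3 thrombocytopenia, grade 4 neutropenia and grade 3 febrile neutropenia.
- Three do so at the second event: grade 2 non-hematological, grade 2 thrombocytopenia and grade 3 neutropenia.

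The count is six if the general rule in 5.3 removing patients for grade 4 treatment-related toxicity overrides the grade 4 neutropenia row. First grade 2 events and a first grade 3 neutropenia resume unreduced by design, so they are not part of this point.

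**The alternative reading.** Applying the Table 3-5 halving on top of level -1 gives 5 × 0.5 = 2.5 mg daily. That is not a dose level, and it cannot be given daily with 5 mg tablets. A patient already at level -1 who then starts a moderate inhibitor meets the same 2.5 mg problem.

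**The return rule, step by step.**
1. The patient takes 10 mg daily.
2. A moderate inhibitor starts: 5 mg daily.
3. A grade 3 toxicity occurs and 5.3 assigns level -1: 5 mg daily, unchanged.
4. The inhibitor stops, and Table 3-5 returns her to the dose before the inhibitor: 10 mg daily.

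She ends on the level 0 dose although 5.3 had assigned level -1, which is 5 mg daily. The same happens if the site had used every-other-day dosing at step 3.

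**Frequency.** Section 1.5 reports that 17 of 35 patients in the earlier single-agent study needed a dose reduction (17/35 = 49%), so reductions are not rare with this drug. That study's reduction rules are not given. No document gives the rate of moderate-inhibitor use, so the number of affected patients cannot be computed.

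**The case against.** The best reply is that the plan already names the missing step. Straight after the halving, Table 3-5 provides for every-other-day dosing to manage toxicity, which describes exactly this patient. Section 5.3 also introduces its algorithm as recommendations, section 4.4 lets the physician stop treatment in the patient's interest, and nothing says the algorithm displaces the more specific interaction rule. This part stands. A reader might infer that such a patient can get no reduction at all, or must be rechallenged unreduced. The documents do not support either, because an unreduced restart is what 5.3 gives when followed alone and not the only course open. Still, the every-other-day step is permissive, has no grade trigger, is not a dose level and is linked to no row of the algorithm.

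Second, same-dose restarts are not foreign to the plan. Section 5.3.2 allows one after hepatitis B reactivation when the patient is already on the lowest protocol dose. That rule is confined to hepatitis B. It shows that the authors considered the dose floor there, while the general algorithm has no counterpart.

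Third, the return rule is plainly meant to reverse the interaction adjustment only, and 5.3 has no re-escalation step after level -1. A sensible site might keep the patient at 5 mg. That is likely the intent, but the wording says otherwise.

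Fourth, exposure to the problem is limited. Table 3-5 advises caution with these inhibitors, and patients receive a list of drugs to avoid. The PgP list in Table 3-7 includes everyday drugs such as captopril, carvedilol and diltiazem. It is not graded by strength, however, and also contains strong CYP3A4 inhibitors, so it is a weak guide to who would be halved. This stands, and it is why no patient count is offered.

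**Conclusion.** The point holds as an unreconciled pair of rules. Under the 5.3 algorithm alone, a patient already halved for a moderate inhibitor gets a 0% cut where a 10 mg patient gets 50%, across seven restart rows (six if the general grade 4 rule governs). Table 3-5 offers a further reduction but leaves it optional and detached from level -1. Its return rule, taken literally, cancels a toxicity assignment made while the inhibitor was in use.

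The dose arithmetic rests only on doses stated in the plan. That few patients are affected is a judgement, since co-medication rates are not given. A reader might also infer some distortion of the CR + PR + SD rate or of the stopping rule. The documents do not support that: the operating characteristics in section 10 do not depend on the dose levels, and no effect on the rate can be derived. Label: cheap improvement (patient safety).

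**What to change.** State in 5.3 and 5.3.5, with a note under the dose modification table:

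- Dose levels are nominal doses in the absence of an interacting drug.
- Level 0 with a moderate CYP3A4 or PgP inhibitor is 5 mg daily, as now. Level -1 with such an inhibitor is 5 mg every other day, including for a patient already at level -1 who starts one.
- When the inhibitor stops, the patient returns to the nominal dose of the level currently assigned (5 mg daily if level -1), not automatically to the pre-inhibitor dose.

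The rules for removal on recurrence stay as they are.

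The cost is a few sentences and one table note by amendment. No visits, patients or tablet strengths are added, because the step works with the 5 mg tablet and is already named in Table 3-5. There are two drawbacks. The pill diary must handle alternate-day dosing, and the documents give no data on 5 mg every other day with an inhibitor.
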